#### 4. STUDY SCHEMA

- Design: AEGIS is an open-label single-arm longitudinal clinical trial to estimate medication adherence and retention in a PrEP HIV prevention program that implements a combination intervention strategy that uses text-messages (iTAB) and a staged adherence counseling support strategy titrated from real-time drug levels in women at-risk for HIV acquisition.
- Duration: Each participant will be on PrEP with medication adherence support for 48 weeks after enrollment with a post study follow-up at 60 weeks. The primary endpoint will be measured at 48 weeks.
- Sample Size: A total of 135 participants will be enrolled (50 at CCTG sites and 85 at the LAC-PATH site).
- Study Population: Eligible participants will include HIV-uninfected cis-gender women at least 18 years of age and who are at risk for HIV acquisition.
- Intervention: All participants will be given PrEP with tenofovir disoproxil fumarate (TDF) + emtricitabine (FTC) fixed dose combination prescribed to be taken once daily. All participants will receive the combined intervention of iTAB text messaging adherence reminders and intensive Next Step Counseling (iNSC). The iTAB system consists of daily, personalized, automated 2-way text messages to maintain adherence and retention, and iNSC is a brief, strengths-based discussion initiated at each clinic visit, typically with delivery of negative HIV-test results, focused on promotion of sexual health protection through behavioral and biomedical (adherence) strategies. Participants that have a low intracellular tenofovir diphosphate (TFV-DP) concentration will receive escalated, targeted adherence support (see study schema). All participants will receive access to PrEP in accordance with standardized comprehensive methods of prescribing and clinical assessments that include safety monitoring as well as regular HIV and sexually transmitted infection (STI) screening.
- Regimen: TDF 300 mg + FTC 200 mg fixed dose combination will be given orally once daily starting at the baseline visit (month 0) and continued throughout the study.

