## 10. RATIONALE FOR ADHERENCE MONITORING

### Real-time dried blood spot intraerythrocytic TFV-DP drug level monitoring

In the iPrEx study, assessments of adherence both by self-report and sensitive drug level assays on blood plasma and PBMCs suggested a strong correlation between adherence to the daily intervention and efficacy (49, 50). The low overall level of adherence to daily pill-taking in the study was striking, with detectable drug found in 9% of seroconverters, and only 51% of non-seroconverters. The medication adherence data is in stark contrast to the overall study retention (86-88% at 48 weeks), and self-reports of medication adherence (95%). Analyses designed to adjust for adherence suggest that if TDF/FTC were taken with fidelity on a daily basis, there could be preventive efficacy of over 90% (8).

The STRAND study established plasma and PBMC steady-state tenofovir (TFV) drug levels achieved from directly observed dosing of TDF/FTC twice weekly, four-times weekly, and 7-times weekly. With twice-weekly dosing, mean PBMC levels were 11 fmol/mL, 4 days per week yielded 32 fmol/mL, and 7 days per week (daily) dosing yielded 42 fmol/mL. In iPrEx, seroconverters had PBMC drug levels on average of 11 fmol/mL, suggesting fewer than two doses per week on average. Non-seroconverters had mean PBMC levels of 16 fmol/mL. A model created from the iPrEx data calculating the protective efficacy which was likely at a given drug concentration in PBMCs demonstrated that the PBMC drug level at which 90% protection would be achieved was estimated to be 16 fmol/mL. Correlating the iPrEx model data with the STRAND data, two doses per week would be estimated to result in 76% (95% CI 56-96%) efficacy; four doses per week, 96% (95% CI, 90- >99%); seven doses per week (daily dosing), 99% (95% CI 96- >99%) (51).

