The main difference between iNSC and targeted iNSC focused on exploring whether or not PrEP is something the participant wants to continue with (given low drug level and relatedly low afforded PrEP benefit), and if so a strengths-based exploration (when dosing did occur, what facilitated it) precedes exploration of specific barriers to dosing (what specifically prevented consistent dosing), needs are identified, strategies discussed and an adherence plan created. Because participants all engage in iTAB, plans will also emphasize use of iTAB to ask for help. Participants no longer interested in PrEP will be engaged in discussion around that decision and their plan for how to stay HIV negative using other strategies discussed.

PrEP-STEPS is a four-session weekly intervention with two subsequent monthly booster sessions modeled after an evidence-based ART adherence intervention (LifeSteps) which is a Cognitive Behavioral Therapy (CBT)-based counseling approach to facilitate PrEP adherence. This program will be deployed at in-person sessions and is the highest intensity level intervention.

The 3 interventions will be used as three “stages” or levels of intensity of adherence support. One intervention is deployed for a given participant, titrated based on the history and chronology of real-time measured DBS TFV-DP levels.

All participants will receive iNSC at the baseline/entry visit and at all subsequent visits [see the MOPS for structure of the standard iNSC intervention]. Suboptimal adherence (TFV-DP levels of <1050 fmol/punch (representing fewer than mean 6-7 daily doses per week)) will trigger “targeted iNSC” which will be implemented when drug levels are obtained by the site- typically about 10 days after the clinic visit (72). Participants in this sub-optimal range are contact by the counselor, informed of their results and asked to come in for a specific conversation (targeted iNSC). This first level of more intensive support may be deployed by telephone or in person. There will not be additional compensation for participating in these sessions. Details of the targeted iNSC intervention are provided in the MOPS. If this is a repeat sub-optimal level the counselor schedules the participant for the first of 4 (+2 booster) PrEP-Steps sessions.

Details of the PrEP-STEPS Program with Content Optimized for Women program are provided in the MOPS.

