**28.2. Permanent Medication Discontinuation**

Permanent medication discontinuation prior to 48 weeks of treatment should be limited to participants who withdraw consent, have laboratory evidence of acute or chronic HIV infection, are so advised by HIV-treatment experts, or have severe toxicity as noted above.

Such participants should continue to be followed per the protocol SOE (Cohort or seroconversion, as appropriate), even though they are no longer taking study medication.

Additionally, participants who have persistently low TFV-DP levels (<1050 fmol/punch), are referred for targeted iNSC (first instance) and PrEP-STEPS (if followed by a suboptimal (<1050 fmol/punch) TFV-DP level at subsequent visit(s)). Refusal/failure to participate in PrEP-STEP programming by attending  $\geq 1$  visit within 30 days of request by study staff may be considered for medication discontinuation in discussion with the Protocol Chairs.

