#### Hypothesis II

Intracellular TFV-DP concentrations levels will correlate with self-reported adherence by daily texting through iTAB,

For the primary analysis, we will measure adherence using a drug level cutoff consistent with 6 or more doses per week, as measured by TFV-DP level > 1050 fmol/punch at weeks 4, 12, 24, 36 and 48. This will be in the as-treated group who are on-PrEP (censoring those on permanent or temporary discontinuation). A descriptive analysis of the proportion of women achieving adequate adherence by week of study will be conducted. Baseline versus 48 weeks proportion of adherence will be compared via Fisher's exact test.

**In order to examine drug adherence surrounding the implementation of intensified interventions specific to women receiving targeted iNSC and those receiving PrEP-STEPS we will compare the change in levels pre- and post-intervention.**

Additional sensitivity analyses will be performed using alternative cutoffs of adherence. Intracellular FTC-TP levels will be compared to TFV-DP for discrepancy of recent dosing that would be reflective of the short half-life of FTC (past day) versus the past week of dosing that is informed by the long half-life of TDF.

Subgroup analysis will compare adherence and other outcomes between risk categories of women (e.g. serodiscordant partnerships with and without conception intentions, partner of elevated HIV risk, sex worker, recent STI, injection drug use, PEP users).

Adherence will be measured by self-report using daily text messaging through iTAB. We will validate iTAB reported adherence in women using the TFV-DP levels for correlation with the proportion of positive responses in the 34 days prior to the drug level (i.e. two half lives of TDF) in week 12, 24, 36 or 48 using the Spearman correlation coefficient.

The average days of adherence per week during this time will be calculated as number of days reporting doses taken in past 35 days divided by 35 multiplied by 7 and rounded to the nearest whole number. For each number of days per week of adherence (i.e. 0, 1, 2,3, 4,

5,6 and 7) the TFV-DP will be reported from mean (95% confidence interval) and median (IQR).

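### The change in TFV-DP around escalated support is read only from women who received it and have a later level; no analysis covers all women whose low level triggered it

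*Combined protocol and SAP*

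**What the plan says.** **The strategy is defined by the drug level.** Section 4: "Participants that have a low intracellular tenofovir diphosphate (TFV-DP) concentration will receive escalated, targeted adherence support". Section 16.5.3 sets the trigger, "Suboptimal adherence (TFV-DP levels of <1050 fmol/punch", and the second stage: "If this is a repeat sub-optimal level the counselor schedules the participant for the first of 4 (+2 booster) PrEP-Steps sessions".

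**The analysis is defined by receipt.** Section 30.2, under Hypothesis II: "specific to women receiving targeted iNSC and those receiving PrEP-STEPS we will compare the change in levels pre- and post-intervention". The plan does not define receiving (for PrEP-STEPS, one session or all of them), does not choose the before and after samples, names no test, and gives no rule for a missing later level.

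**Non-receipt is foreseen.** Section 16.5.3 says that a woman who declines the adherence interventions may be considered for stopping PrEP. Section 28.2 has a similar provision, beginning "Refusal/failure to participate in PrEP-STEP programming by attending", for women who attend no PrEP-STEPS visit within 30 days of being asked. Targeted iNSC is itself "focused on exploring whether or not PrEP is something the participant wants to continue with", so a decision to stop is one foreseeable result of it.

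**Follow-up continues after stopping.** Section 28.2 keeps women who permanently discontinue on the schedule of evaluations. Table 1 lists dried blood spots at week 4, week 12 and every 12 weeks after that, and at end of study or premature discontinuation.

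**Status of the section.** Section 30 describes itself as brief and defers to a formal SAP, to be finalised before database lock, which takes precedence.

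**The concern.** The natural question about escalation is what happened to the women whose low level set it off. The planned comparison answers a narrower one: how levels moved in women who took up the support and were sampled again. Refusing, not attending and leaving all happen after the trigger, and all are plausibly related to poor adherence, so the women left out are unlikely to resemble those kept.

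This is the only planned comparison that looks at the drug-level-titrated part of the package separately from the rest of the programme. A clear mean rise could be reported while a sizeable share of triggered women never took up the support, and nothing in section 30.2 would show that share. Acceptability and feasibility are to be measured on a Likert scale, so uptake among triggered women is not a planned output either.

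**Working it through.** The plan states no figure for this comparison, so there is none to reproduce. Its one precision statement (section 30.1, 90% ± 6% with 100 women) does reproduce, as 1.96 × √(0.9 × 0.1 / 100) = 5.88 points, but it concerns the proportion above 1050 and not this change.

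**1. Who is counted.** Setting sections 16.5.3, 28.2, 30.2 and Table 1 side by side, a triggered woman is in one of these positions:
- received support and has a later level: in;
- refused or did not attend: out, because the set is women receiving support;
- received support but left before the next sample: out, because no change can be computed;
- received support, stopped PrEP, still followed: a sample is scheduled, but the plan does not say whether it is used.

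**2. Formula.** Let f be the share of triggered women omitted, and D_in and D_out the mean changes in included and omitted women.
- D_all = (1 − f) × D_in + f × D_out
- Bias = D_in − D_all = f × (D_in − D_out)

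The bias is zero if both groups change equally, and reverses if omitted women improve more.

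**3. Size when omitted women do not change (D_out = 0).** Relative overstatement = D_in / D_all − 1 = f / (1 − f). The documents give no f, so these values are assumptions:
- f = 10%: 0.10 / 0.90 = 11%
- f = 20%: 0.20 / 0.80 = 25%
- f = 30%: 0.30 / 0.70 = 43%

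**4. How much depends on women who stop PrEP.** Assume a level of 700 fmol/punch before support and D_in = 200. With the 17-day half-life in section 10, a woman who stops straight after the first sample changes by 700 × (2^(−84/17) − 1) = 700 × (0.033 − 1) = −677 over 12 weeks.

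| f | D_all, omitted women unchanged | D_all, omitted women stopped |
|---|---|---|
| 10% | 180 | 112 |
| 20% | 160 | 25 |
| 30% | 140 | −63 |

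In the last column the rise of 200 vanishes at f = 200 / (200 + 677) = 23%. That column applies only if the later levels of women who stop are missing or not used, which is the point left open in step 1.

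**5. Why a trigger-defined figure is still not an effect.**
- Accumulation: with constant dosing from baseline, the level is 1 − 2^(−28/17) = 68% of steady state at week 4 and 1 − 2^(−84/17) = 97% at week 12, a 1.42-fold rise. A woman at 1352 at week 12 (the mean quoted in section 16.5.2) would be near 1352 / 1.42, about 951, at week 4. She would be triggered and then pass 1050 with no change in behaviour.
- Selection on a low level: in a simulation with no effect of support, assuming normal levels with mean 1352, between-woman SD 300 to 400 and within-woman SD 200 to 300, triggered women rose by 114 to 276 on average.

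**The case against.** **A reader might infer that women who stop PrEP drop out of the comparison.** The documents do not say so. Section 28.2 keeps them in follow-up and Table 1 schedules their samples. The on-PrEP restriction, "This will be in the as-treated group who are on-PrEP (censoring those on permanent or temporary discontinuation", is written for the primary analysis and is not extended to this one. If their later levels are used, their falls lower the mean change. What stands is that the plan is silent. The exclusion of refusers and non-attenders does not depend on this.

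**A reader might take f from section 10, which cites "overall study retention (86-88% at 48 weeks" in the trial in men who have sex with men, as 12% to 14%.** That is cumulative loss over 48 weeks in another population. Women lost before any trigger never enter the set, and women lost after their later sample still count. Levels from weeks 4 to 36 are analysed in real time (section 25), so the next visit is 8 to 12 weeks after the trigger sample. At constant loss, 1 − 0.88^(12/48) = 3.1% and 1 − 0.86^(12/48) = 3.7% per 12 weeks, which gives an overstatement of only 3% to 4%. Loss among triggered women could be higher, but the documents give no figure.

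**Stakes.** Escalation is not a named objective or hypothesis, and section 30.2 presents the comparison as an examination of adherence around the interventions, not as an effect estimate. Retention, and factors associated with loss and discontinuation, are reported elsewhere. This is fair and limits the consequence. But those outputs are not tied to the trigger and do not correct this comparison.

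**Uptake may be high.** Targeted iNSC can be given by telephone, which may keep non-receipt low at the first stage. PrEP-STEPS is in person, with four sessions and two boosters, so the argument is weaker there.

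**The formal SAP may settle this.** It may, and that is why the change is cheap now.

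**Conclusion.** The point holds as a gap in the analysis set. Inclusion depends on receipt and a later level, the strategy depends on the trigger, and no planned analysis covers all triggered women.

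It would go too far to say that the rise is overstated. Upward bias is the likely direction, because women who refuse or leave would be expected to do worse, but nothing in the documents shows it. The 11%, 25% and 43% rest on assumed shares of 10%, 20% and 30% and on no change in the omitted women. The size is larger if those women fall, and nil if they change as the others do. Nor would a trigger-defined set show that acting on a low level works: there is no comparator, and levels can rise without any change in behaviour.

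The primary proportion above 1050 by week is not affected. This is an inexpensive improvement that should be made before the SAP is finalised.

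**What to change.** In the SAP:
- **Main set:** every woman with a first TFV-DP below 1050 fmol/punch (targeted iNSC) and, separately, every woman with a repeat level below 1050 (PrEP-STEPS), whether or not the session took place.
- **Levels:** use all later dried blood spot results regardless of PrEP status. Define the before and after samples and what counts as receiving each intervention.
- **Outcome at the next scheduled visit:** place each triggered woman in one of four groups: on PrEP above 1050, on PrEP not above 1050, stopped PrEP, or no sample. Give the first as a proportion of all triggered women with a 95% confidence interval.
- **Counts:** numbers triggered, receiving support and with a later level, at each stage.
- **Week 4:** show week-4 triggers separately, because levels are still accumulating.
- **Supportive result:** keep the change among receivers, labelled as conditional on attendance and a later sample.
- **Interpretation:** state that neither figure is an effect estimate, because there is no comparator and women are selected on a low level.

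The cost is SAP wording and slightly more reporting. Sites already need the level and the attendance record to run the escalation steps and the 30-day provision in section 28.2, and section 29.2 lists medication use among the data collected. The one downside is a less favourable headline figure.

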### **16.5.1. Real-time intraerythrocytic drug levels**

Blood will be collected for intraerythrocytic TFV-DP drug level assays at each follow-up visit. Prior pharmacokinetic/pharmacodynamics studies have established levels for categorization of dosing for interpretation of DBS levels. Given the high adherence requirement for women to achieve protective levels, a threshold of 1050 fmol/punch corresponding to 6 or more doses per week will be used as the threshold for optimal adherence (28, 60). Levels below this threshold will be considered to represent suboptimal adherence and will trigger intensification of adherence support as outlined below.

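### The pre/post TFV-DP comparison has no allowance for time on drug: for targeted iNSC triggered at week 4, accumulation alone adds about 42% by week 12

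*Combined protocol and SAP*

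**What the plan says.** Section 30.2 (under Hypothesis II) gives the analysis of the stepped-up support in one sentence: for women receiving targeted iNSC and "those receiving PrEP-STEPS we will compare the change in levels pre- and post-intervention". I read 'levels' as TFV-DP. The sentence does not say which visit is 'pre', which is 'post', how time on drug is handled, or what statistic is used.

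Women enter the comparison through a low level. Section 16.5.1 sets "a threshold of 1050 fmol/punch corresponding to 6 or more doses per week" and states: "Levels below this threshold will be considered to represent suboptimal adherence and will trigger intensification of adherence support". The same cutoff serves every visit. Under Section 16.5.3, targeted iNSC follows when the result reaches the site, "typically about 10 days after the clinic visit", and a repeat low level leads to PrEP-STEPS. On length, "PrEP-STEPS is a four-session weekly intervention with two subsequent monthly booster sessions".

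Drug starts at baseline (Section 4). In Table 1 (Section 20) the dried blood spot is first drawn at week 4, and Section 25 lists weeks 4, 12, 24 and 36 for real-time assay. Section 10 gives a 17-day half-life for TFV-DP in red blood cells.

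Elsewhere Section 30.2 does restrict the visits it uses. The text-message correlation takes responses "in the 34 days prior to the drug level (i.e. two half lives of TDF) in week 12, 24, 36 or 48", which leaves out week 4.

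**The concern.** With a 17-day half-life, TFV-DP is still building at week 4. A woman who takes her tablets in the same pattern throughout will have a clearly higher level at week 12. If she was flagged at week 4, the rise lands in the 'post' sample and looks like a response to counselling. There is no comparison arm to show otherwise.

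Selecting women on a low reading also invites regression to the mean. Part of any low reading is chance, so the next one tends to be higher even with no counselling effect.

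This is the only comparison in the plan aimed at the stepped part of the programme. The risk is that a rise which would occur anyway is taken as support for stepping up.

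**Working it through.** **Inputs.** Half-life 17 days (Section 10). Dosing from day 0, at baseline (Section 4). Week 4 = day 28, week 12 = day 84, week 24 = day 168. Trigger below 1050 fmol/punch (Section 16.5.1). A mean of 1352 fmol/punch at week 12 in the cited text-messaging trial, equated there to 6 of 7 doses (Section 16.5.2).

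**The plan's own figure.** Section 30.2 calls 34 days two half-lives: 2 × 17 = 34. The analysis section and Section 10 therefore use the same half-life.

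**Accumulation at constant dosing** (my assumption: first order, starting from zero). Fraction of steady state f(d) = 1 − 2^(−d/17).

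- f(28) = 0.681, f(84) = 0.967, f(168) = 0.999
- Week 4 to 12: f(84)/f(28) = 1.421, a rise of 42%
- Week 12 to 24: f(168)/f(84) = 1.033, a rise of 3%
- Week 24 to 36: 0.1%; later, about 0%

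**Visit window.** Table 1 shows ±14 days, but its column alignment is unclear in the text I have, so this is a sensitivity check.

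| First sample | Second sample | Rise |
|---|---|---|
| day 42 | day 70 | 15% |
| day 28 | day 84 | 42% |
| day 14 | day 98 | 126% |
| day 70 | day 182 | 6% |

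**What would cancel it.** The week-12 level equals the week-4 level only if dosing after week 4 runs at 0.681 of its earlier rate, a fall of about 32%.

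**Who is affected.** Take steady 6-of-7 dosing anchored to 1352.

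- If 1352 is the steady-state value: week 4 is 1352 × 0.681 = 920 and week 12 is 1352 × 0.967 = 1308.
- If 1352 is the week-12 value: steady state is 1352/0.967 = 1397, week 4 is 951 and week 12 is 1352.

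Either way such a woman reads below 1050 at week 4, is flagged, and then appears to gain 388 to 401 fmol/punch with no change in pill-taking. In general, a week-4 level between 1050/1.421 = 739 and 1050 passes 1050 by week 12 at constant dosing.

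**PrEP-STEPS.** It needs a repeat low level, so on scheduled visits its own trigger is week 12 at the earliest and accumulation adds about 3%. If instead the first, week-4 low level were the 'pre', then f(168)/f(28) = 1.467, a rise of 47% to week 24.

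Its 'post' is also open. Suppose the first session falls 10 days after the trigger visit, or 40 if a further 30 days pass; Section 28.2 says that failure to attend a "visit within 30 days of request by study staff may be considered for medication discontinuation". The fourth session is 21 days after the first (day 31 or 61). The second booster is 56 days later, taking 28-day months (day 87 or 117). The next visit is nominally day 84.

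**Regression to the mean.** Its size needs the spread of levels between women and the within-woman correlation between visits. The documents give neither for this population, so I put no figure on it.

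**The case against.** The best reply is that Section 30 is only a brief description. A formal SAP, to be finalised before database lock, will carry the detail and takes precedence. It is not among the documents, nor is the MOPS. The comparison supports no stated objective or hypothesis, names no test and makes no causal claim. All of that stands and limits the weight of the point. It does not remove it: with no baseline spot, a comparison of scheduled samples for week-4 triggers carries the rise unless something is done about it. A level at the time counselling is delivered (day 38) would cut the rise to 23%, but no sample is scheduled then.

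A reader might infer three stronger things that the documents do not support.

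- *That the 42% applies to both interventions.* It belongs to targeted iNSC triggered at week 4. It reaches PrEP-STEPS only if a week-4 level is used as its 'pre'.
- *That most first low levels must arise at week 4.* That depends on assumed inputs. Some assumed distributions put 70% to 100% of first lows there. With steady-state means of 1577 to 1630 (perfect dosing, 7/6 of 1352 and 1397), an SD of 300 or 400, correlation 0.5 to 0.9 and a 20% fall per visit, the share is 41% to 53%.
- *That taking the next visit as 'post' is a demonstrated fault for PrEP-STEPS.* At the early end the overlap is three days, on assumed 28-day months, and all four weekly sessions are over by day 31 to 61. It is a reason to define 'post', no more.

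**Conclusion.** The concern holds for targeted iNSC triggered at week 4. The planned change in TFV-DP then includes a rise of about 42% from accumulation alone, or about 15% to 126% if a ±14-day window applies to both visits. This rests on the 17-day half-life, first-order accumulation from zero and constant dosing from baseline. The first is the protocol's figure; the other two are assumptions. For pairs starting at week 12 or later, accumulation is about 3% (up to about 6% within the windows) and can be ignored in practice.

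Regression to the mean pushes the same way at every trigger, by an amount that cannot be computed from the documents. A raw rise in this comparison is therefore not evidence that the added counselling worked. The analysis is supporting and descriptive, so this is something the SAP should correct rather than a threat to the primary result.

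**What to change.** In the formal SAP:

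1. For targeted iNSC, take the triggering level as 'pre' and the next scheduled visit as 'post', as within-woman pairs. Report week-4 triggers separately from later ones.
2. Report the raw change, and beside it the change after dividing each level by 1 − 2^(−days since starting drug/17), using actual dates. Vary the half-life: over an assumed 12 to 22 days the week-12/week-4 ratio is 1.238 to 1.585, against 1.421, so the rescaled ratio moves by −13% to +12%. As further sensitivity analyses, exclude week-4 'pre' levels, following the visit restriction already used for the text-message correlation, and exclude women with a recorded interruption, for whom days since starting overstates exposure.
3. For PrEP-STEPS, set 'post' by scheduled visit counted from the triggering visit, for example both the next and the following one, for every woman referred. Waiting for the last booster would turn it into a completers-only comparison. A week-36 trigger has only week 48 after it. Report session attendance and the number without a 'post' level. State whether the primary analysis restriction, "This will be in the as-treated group who are on-PrEP (censoring those on permanent or temporary discontinuation", also applies here, since it decides who has a pair.
4. State that regression to the mean remains and that the change is not evidence of a counselling effect.

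The cost is SAP wording and a few lines of code on data already planned. No visit, sample or trigger changes. The rescaled figure relies on the 17-day half-life, and the change will look less favourable.
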